### **C.20.c. Patient Cost and Utilization.**

All resource utilization and cost data will come from Decision Support System (DSS) data (or equivalent database if the VA data storage locations change before the end of the study), including the DSS Outpatient (OPAT) National Data Extract (NDE), the DSS NDE SAS Pharmacy Dataset, and the DSS Inpatient Discharge Extract File (DISCH). We will measure VA outpatient and inpatient utilization and costs by treatment or control over 18 months. Outpatient encounters will be categorized using clinic stop codes into primary care visits, specialty care visits, and other outpatient care (laboratory, radiology, surgery, nursing, and all other clinical visit and ancillary services and encounters not already mentioned), as well as a count of total encounters (unique CLSTOPS) and total costs (OCST\_TOT). We will also examine hypertension-related outpatient pharmacy prescription counts and costs using an identification method developed in the HINTS study (SAS algorithm of HTN-related outpatient drugs developed by [name], Puget Sound VA), in order to compare them to total outpatient pharmacy costs (DISP\_COST plus ACT\_Cost). The utilization most likely to be affected by the intervention will be outpatient and pharmacy-related. For comparability with other studies, however, we will also examine inpatient utilization and costs. Inpatient encounters will include whether there was any inpatient care in the study period, total days in the hospital (DISDAY minus ADMITDAY, DAYS), and total inpatient costs (DCST\_TOT). We will also use diagnostic codes to categorize inpatient stays that are hypertension related. The analysis will focus on differences in utilization and costs in the study period but we also will examine costs in the 18 months pre-intervention to check for temporal trends. Specific variables outlined above represent applicable variables as of the time of the initial protocol submission. Because of changing VA data structures, the precise variable names may change over the course of the study. In addition we will evaluate costs from the perspective of both patient and society.

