### D.3. Sample Size and Power Considerations

The sample size estimate is based on the primary hypothesis: veterans randomized to titrated disease management will have lower mean systolic blood pressure at 18 months than veterans randomized to bi-monthly LPN-delivered telephone calls. A 5 mmHg improvement at 18 months will be the definition of a minimally clinically significant difference. This represents the differential between the two treatment groups at 18 month; therefore, the power and sample size considerations, apply even if the control group also improves over the 18 month study period (i.e., "placebo" effect). For example, if the control group improves from 145 mmHg to 142 mmHg, we will have adequate power to detect a 5 mmHg differential improvement – the intervention group improves from 145 to 137 mmHg.

Sample size calculations are based on ANCOVA methods as presented in Borm et al. We used data from previous studies to estimate quantities needed for the sample size calculation. We anticipate a common mean systolic blood pressure of 145 mmHg, a standard deviation of 17.5 mmHg in both treatment groups at baseline, and a correlation between time points equal to 0.4. Finally, based on previous studies, we estimate a 15% attrition rate by 18 months. From the calculation, we determined that **we will need to enroll until we randomize 400 patients (200 randomized in each group)** to detect a 5mmHg difference at 18 months with 80% power and a type-I error of 5%. Based on our prior recruitment experience, we consider this to be feasible given the 18 months timeframe (on average 6-7 patients per week), the potential for over 3,800 eligible individuals in Durham and a total of ~7,900 in all Durham affiliated clinics, and the requested resources. We note that these calculations do not reflect that stratification variables will be included in the final analysis model described above. Stratification variables are expected to account for variability in the outcome. The projected sample size analysis is therefore conservative, and we anticipate that there will be greater power to detect between-group differences with this study size.

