##### D.6.b. Analysis.

The primary objective of the cost-effectiveness analysis will be to estimate the cost per unit difference in effectiveness. The incremental cost effectiveness ratio (ICER) will be calculated as the difference in the average cost per patient between the treatment and control arm divided by the difference in the units of mmHg between the treatment and control arms:

$$ICER = \frac{AVERAGE\ COST_{t=x} - AVERAGE\ COST_{t=0}}{Average\ Reduction\ mmHg_{t=x} - Average\ Reduction\ mmHg_{t=0}}$$

Because we will take an all-cost approach, that is, we assume that any costs unrelated to blood pressure or the intervention will be neutral between the treatment and control group, we will carefully examine the data for outliers. For example, there may be high inpatient costs for patients in the intervention group that are attributable to non-hypertension related comorbidities, necessitating a consideration of this in the analysis. As such, in addition to a consideration of all resource utilization costs described, we will run sensitivity analysis in which we will (1) use diagnostic codes in the inpatient files in order to attribute inpatient utilization to treatment of comorbidities associated with chronic hypertension and/or diabetes, running a sub analysis only on this type of inpatient care; (2) remove patients who are outliers and (3) consider outpatient costs and outpatient HTN-related pharmacy costs exclusively. In addition, we will also perform sensitivity analysis of the ICER calculated on two samples: all patients randomized (complying with the intention to treat principles and a subset of all patients who completed the intervention. Sensitivity analyses will also be performed on types of costs: intervention costs, resource utilization costs, and total costs (intervention costs plus resource utilization costs). If there are no differences in resource utilization across arms, we will simply include the intervention

costs in the ICER calculation. All dollars will be expressed in 2011 dollars, using the Consumer Price Index for Medical Care for medical items or Consumer Price Index for other items.

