We will use stochastic methods to evaluate variability associated with the cost-effectiveness ratio. If the difference in SBP is significantly higher in an intervention arm relative to the standard care arm, the 95% confidence interval for the base-case cost-effectiveness ratio will be computed with nonparametric bootstrapping using the bias-corrected percentile method (1,000 repetitions). The bootstrapping procedure will allow us to use limited information to estimate the sampling distribution of mean costs per patient, which then will allow us to make inference about the true population sampling distribution of mean costs without making strong distributional assumptions. Using bootstrapped confidence intervals will help us bind our estimates in a way that reduces the influence of outliers. This procedure is relevant for thinking about implementation effects of the intervention, when there will be much larger sample sizes and a ICER not limited by small sample properties.

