#### **D.9. Exploratory Analyses**

We will also examine predictors/covariates that may explain for which individuals the intervention is more effective. For example, prior work suggests that African Americans are more likely to have greater improvements in SBP/DBP than whites participating in diseases management studies. These analyses may include examining the impact of the intervention on additional clinical outcomes available through the VA electronic health record or related linked administrative data (e.g. impact of the intervention of hemoglobin A1c for patients with diabetes).

We will also collect data via the VA electronic health record or related linked administrative data on healthcare events for the full sample from the study. While we are not likely to be powered to detect differences in healthcare events, these analyses may provide preliminary data and power calculations for future studies. These data will also allow for long-term examination of the impact of the intervention on clinical and economic outcomes. With appropriate informed consent and HIPAA authorization, clinical and utilization data from VA electronic health record or related linked administrative data may be obtained for the period prior to or after study enrollment.

Linked data that may be obtained with appropriate informed consent and HIPAA authorization includes information from linked Medicare and/or Medicaid files for patients with corresponding healthcare coverage.

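### The rule that drops utilisation costs from the ICER after an undefined finding of no difference can bias the base case and leave utilisation-cost uncertainty out of its interval

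*Protocol*

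**What the plan says.** Protocol section D.6.b defines the ICER as the difference in average cost per patient between arms, divided by the difference in SBP reduction. The costing is described as comprehensive: "Because we will take an all-cost approach". Near the end of the same paragraph the numerator becomes conditional: "If there are no differences in resource utilization across arms, we will simply include the intervention" costs in the ICER. The section does not say how a lack of difference is to be judged, or whether on encounter counts, on costs, or within a category of care.

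The paragraph also plans alternatives: "Sensitivity analyses will also be performed on types of costs: intervention costs, resource utilization costs, and total costs". For uncertainty, the section says that, if the SBP difference is significant, "the 95% confidence interval for the base-case cost-effectiveness ratio will be computed with nonparametric bootstrapping using the bias-corrected percentile method", with 1,000 repetitions. No interval is stated for any other version of the ratio.

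Two other sections bear on the rule. Section C.20.c says "The utilization most likely to be affected by the intervention will be outpatient and pharmacy-related". Section D.9, on exploratory analyses, concedes "While we are not likely to be powered to detect differences in healthcare events".

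**The concern.** Two arm means are practically never equal, so the rule needs some threshold to operate, and the usual working threshold is a non-significant test. Under that reading the base-case numerator is chosen by a pre-test on the trial's own data. When the test is not significant, the estimated utilisation difference is replaced by zero and its variance disappears from the bootstrap.

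This contradicts the all-cost approach stated in the same paragraph, and the aim in section C.20.b of measuring both intervention and utilisation costs so as to see what system-wide adoption would cost. It can also remove the outpatient and pharmacy costs that section C.20.c expects the intervention to move. At stake is the answer to H3: the headline cost per mmHg could be wrong in level and look more precise than the data allow.

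**Working it through.** **Inputs from the protocol.** Section D.3: "we will need to enroll until we randomize 400 patients (200 randomized in each group"), a 5 mmHg difference, SD 17.5 mmHg, correlation 0.4, 15% attrition, 80% power, type-I error 5% (taken as two-sided). Intervention costs come from the earlier trials in section B.7 and Table 1, scaled to 18 months:
- $112 per patient-year × 1.5 = $168.
- $416 over 24 months × 0.75 = $312. Table 1 gives the same $416 per year, which would be $624.
- About $460 per patient-year × 1.5 = $690.

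**Assumptions.** The protocol gives no SD for utilisation cost, so S is varied. The SD of intervention cost is set at half its mean. A lack of difference is read as p ≥ 0.05.

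**The plan's own figure.** No cost figure is stated to reproduce. The sample size does reproduce: ANCOVA SD = 17.5 × √(1 − 0.4²) = 16.04; n = 162 per arm; 162/0.85 = 191 per arm, 382 in total. With 400 randomised and 170 per arm retained, power is 82%. The standard error (SE) of the SBP difference is 16.04 × √(2/170) = 1.74 mmHg.

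**Step 1: what a utilisation comparison can detect.** SE = S × √(2/200) = S/10. The 95% half-width is 1.96 × SE, and the difference detectable with 80% power is 2.80 × SE.

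| Assumed S | SE | 95% half-width | Detectable at 80% power | Power for a true $500 |
|---|---|---|---|---|
| $2,000 | $200 | $392 | $560 | 71% |
| $5,000 | $500 | $980 | $1,401 | 17% |
| $10,000 | $1,000 | $1,960 | $2,802 | 7.9% |
| $20,000 | $2,000 | $3,920 | $5,603 | 5.7% |

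From about $5,000 upwards, a non-significant result is compatible with differences larger than the whole intervention cost.

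**Step 2: bias when the term is dropped.** With a $312 intervention cost and a 5 mmHg effect, the intervention-only ICER is 312/5 = $62 per mmHg. If utilisation truly rises by $500, the total-cost ICER is 812/5 = $162. If it falls by $500, the ICER is −188/5 = −$38.

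**Step 3: interval width.** Simulated with a 5 mmHg effect (SE 1.74), a $312 intervention cost and a true utilisation difference of zero. The intervention-only interval is about $37 to $190 per mmHg.

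| Assumed S | Total-cost interval ($ per mmHg) | Width relative to intervention-only |
|---|---|---|
| $500 | 32 to 193 | 1.06 |
| $1,000 | 20 to 206 | 1.2 |
| $2,000 | −18 to 243 | 1.7 |
| $5,000 | −164 to 389 | 3.6 |
| $10,000 | −427 to 646 | 7.0 |

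Over S from $500 to $30,000, the ratio runs from 1.2 to 38 at an intervention cost of $168, and from 1.01 to 9.4 at $690.

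**Step 4: coverage under the rule.** Trials were simulated with 200 per arm, no attrition, lognormal costs and 400 percentile-bootstrap draws, keeping those with a significant SBP result. The target is the true total-cost ICER. A repeat run agreed to within about 5 percentage points.

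| Assumed S | True difference −$500 | True difference +$500 |
|---|---|---|
| $2,000 | 74% | 80% |
| $5,000 | 17% | 51% |
| $15,000 | 4% | 43% |

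With a true difference of zero, the rule covers 92% to 95%. Always keeping utilisation costs covers 94% to 97% in the settings of the table. The asymmetry follows from step 2: −$38 lies outside the typical intervention-only interval, whereas $162 lies towards its upper end.

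**The case against.** The strongest reply is that the pre-test is inferred. Section D.6.b names no significance test, and how a lack of difference is judged might be settled in an analysis plan. That stands as a limit on the coverage figures, which assume p ≥ 0.05. It does not rescue the rule, because any data-driven threshold would still set an estimated quantity to zero and discard its uncertainty.

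Second, the rule speaks of utilisation, which section C.20.c measures in several ways. Visit or prescription counts may have different power from total cost, so the documents do not show that the comparison would usually find nothing.

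Third, a reader might infer that the interval must be far too narrow. The documents do not support that. They give no cost SD, the width ratio is close to 1 at low SDs, power for $500 is 71% at an SD of $2,000, and coverage is near nominal if the true difference is zero. The intervention costs are also borrowed from programmes with contact every two months, while this trial uses monthly nurse or pharmacist calls against an active control.

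Fourth, intervention, utilisation and total-cost ICERs are all planned as sensitivity analyses, so a real saving or added cost would be visible. This stands as mitigation, but no interval is stated for them.

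A reader might also fault making the interval conditional on a significant SBP difference. Sections A.1.c and D.6 pose the cost-effectiveness question only if the intervention works, so that condition follows the protocol's own question and is not part of this point.

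**Conclusion.** The point holds as a fault in a stated rule, not as a missing detail. An undefined, data-dependent condition can remove utilisation costs from the base case, against the all-cost approach in the same paragraph. If true utilisation differs between arms, the base-case ICER is biased: by $100 per mmHg for a $500 difference at a 5 mmHg effect, when the term is dropped. Its bootstrap interval also omits utilisation-cost uncertainty.

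The direction of the problem is clear, but its size is not fixed by the documents. It rests on the assumed cost SD, the borrowed intervention cost, and reading the condition as non-significance. It ranges from negligible at low SDs or a true zero difference to severe undercoverage at SDs of $5,000 and $15,000 with a true $500 difference. The primary analysis is unaffected. H3, a secondary hypothesis, is the one exposed, so the change should be made but does not call the trial into question.

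**What to change.** In section D.6.b:
- Delete the sentence that limits the ICER to intervention costs when utilisation does not differ.
- State that the base-case numerator is total cost, intervention plus utilisation, whatever any comparison of utilisation shows.
- Keep the intervention-cost-only ICER as a labelled sensitivity analysis.
- State that the bootstrap for the total-cost base case resamples patients within arm, carrying each patient's costs and SBP together.

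This needs no new data, since utilisation costs are already to be collected under section C.20.c. The cost is a wording change, minor analysis work and a wider reported interval.

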#### **D.7. Missing Data**

Because the main predictors of interest, treatment group and demographics, are collected at baseline, we do not anticipate much missing data in these variables. There may be missing values in the outcome measures due to drop-out, a missed interim assessment, or item non-response. Given a thorough understanding of the missing data mechanism, it is possible to use all of the available information in analysis, rather than using only subjects with completely observed information. Our main analysis technique, general linear models via maximum likelihood estimation, implicitly accommodates missing data when the response is Missing At Random (MAR); that is, when missing data is due either to treatment, to prior outcome, or to other baseline covariates included in the model. Therefore, inferences will be valid even if we have differential dropout by treatment group. Depending on the type and scope of missing data, we will also explore multiple imputation as a strategy to use in conjunction with our primary analytic tools. Finally, following recent guidelines published by the National Research Council's Panel on Handling Missing Data in Clinical Trials, we will conduct sensitivity analyses with sets of pattern-mixture models to examine the degree to which our primary analyses and inferences are dependent upon missing data assumptions.

#### **D.8. Intention-to-Treat Analysis**

All of the proposed primary and secondary analyses focus on the effect of the intervention group as compared to the control group. We, therefore, plan to use the Intention-to-treat assumption for all analyses. In this assumption, patients are analyzed as part of the group to which they are randomized, regardless of treatment compliance.

#### **D.9. Exploratory Analyses**

We will also examine predictors/covariates that may explain for which individuals the intervention is more effective. For example, prior work suggests that African Americans are more likely to have greater improvements in SBP/DBP than whites participating in diseases management studies. These analyses may include examining the impact of the intervention on additional clinical outcomes available through the VA electronic health record or related linked administrative data (e.g. impact of the intervention of hemoglobin A1c for patients with diabetes).

We will also collect data via the VA electronic health record or related linked administrative data on healthcare events for the full sample from the study. While we are not likely to be powered to detect differences in healthcare events, these analyses may provide preliminary data and power calculations for future studies. These data will also allow for long-term examination of the impact of the intervention on clinical and economic outcomes. With appropriate informed consent and HIPAA authorization, clinical and utilization data from VA electronic health record or related linked administrative data may be obtained for the period prior to or after study enrollment.

Linked data that may be obtained with appropriate informed consent and HIPAA authorization includes information from linked Medicare and/or Medicaid files for patients with corresponding healthcare coverage.

## **E. POTENTIAL DIFFICULTIES AND LIMITATIONS**

We are proposing to randomize 400 individuals. However, based upon our prior experience, we will be able to achieve our recruitment goals using multiple techniques established in our prior studies: 1) the Durham VAMC has a large pool of potentially eligible patients (~7,900 patients, including ~3,800 in Durham based on most recent quality improvement figures); 2) the COE's research assistants have experience working with veterans and have worked with the VAMC clinics previously; 3) all material has been examined for culturally sensitivity. These methods and past experience have led to very high recruitment rates in previous studies and surpass the proportion of minorities and vulnerable individuals found in the local community. An additional challenge is the number of intervention components that individuals may receive including both behavioral and medication management. In general, evidence does not suggest 'one size fits all' and in the context of hypertension, there are a number of behaviors involved that patients need to address. We propose to examine the use of specific components of the intervention.

## **F. STUDY STRENGTHS**

Although several clinical trials have demonstrated the efficacy of utilizing various combinations of behavioral phone calls, home monitoring, and pharmaceutical management in reducing systolic blood pressure, these previous studies relied on single protocols for all patients in the studies that did not vary based on patient outcomes during the study. While very appropriate for efficacy studies aimed at establishing evidence for new interventions, these traditional methods do not necessarily answer the key question of whether it is possible to titrate the resource intensity of such disease management components as would be done in clinical practice. As a result, we are proposing a pragmatic clinical trial of titrated disease management. In a pragmatic trial, clinicians must follow a specific protocol (e.g., titration algorithm, standardized scripts for phone calls, medication management algorithms). However, specific patients will receive services that are in line with the protocol, not specifically the same exact services or drugs. This more closely approximates clinical care.

As described in section B.7, the study team has extensive experience conducting disease management trials. Previous projects demonstrate an ability to: 1) recruit patients; 2) follow patients through the intervention, and 3) analyze results. We look forward to extending previous work through a pragmatic trial aimed at addressing a question critical to the VA: can we develop a system for titrating the resource intensity of disease management so that patients receive appropriate care within resource constraints?

## **G. DISSEMINATION OF STUDY RESULTS**

The proposed research recognizes that healthcare systems have limited resources to meet the many goals involved in helping patients. The purpose is to examine whether having a titrated disease management program based on clinically reasonable triaging criteria leads to better disease control than booster behavioral telephone calls conducted on top of usual care. As a result, the proposed research is designed with potential implementation in mind and holds promise for improving patients' CVD control and meeting the VA's BP goals. For the research to have an impact, stakeholders, and those in position to effect change based on the work, must be aware of projects from initiation through publication. This sets the stage for rapid more widespread implementation of resulting innovations in care. In the case of the proposed study, like others conducted by this research team, ongoing dissemination throughout the project will allow other researchers engaged in intervention research to learn from experiences of the research team.

We have attached letters of support from representatives of the Stroke, Diabetes, and Ischemic Heart Disease QUERIs and Durham VAMC Associate Chief of Staff for Ambulatory Care. In addition, the Co-Clinical Coordinator of the IHD QUERI is a co-investigator ([name]). The established relationship with these groups will allow us to consult with QUERI leadership on the process of implementing study and actively building relationships with VA stakeholders should the intervention under study prove to be effective. In our own facility, we will work with the ACOS for Ambulatory Care to plan for how our project may impact to workflow of the clinic, increasing both the likelihood of successful conduct of the trial and future implementation. We have also attached a letter of support from the national director of VA clinical cardiology supporting the intervention as one that should be considered for widespread implementation should it be effective/cost-effective.

The study team has a great deal of implementation experience in and outside of the VA. For example, the PI served as served as the Project Director for the treatment measurement aspects of the Colorectal Cancer

Care Collaborative (C4). C4 was a partnership between Health Services Research & Development, Office of Quality and Performance, Systems Redesign (formerly Advance Clinic Access) program, Office of Patient Care Services, and Office of the Deputy Under Secretary for Operations and Management. [name] also conducted analysis of data for a special study of the VA External Peer Review Program (EPRP) on the quality of colorectal cancer care. In addition, Drs. [name] and [name] are conducting the Hypertension Telemedicine Nurse Implementation Project for Veterans (HTN-IMPROVE) project which is seeking to understand the process of implementing nurse-delivered telephone self-management support in three VA Medical Centers (funding of surveys and qualitative interviews via RRP-09-198, [name], PI; [name], Co-PI). We are also conducting a study to examine longer-term outcomes of previous clinical trials so that we can better understand potential patient needs that may surface during the implementation of self-management support programs (funded via RRP-09-407, [name] PI; Drs. [name] and [name], Co-Is).

Results from this grant will be disseminated in journal articles, other written reports, and presentations at national, state, and local conferences and meetings.

